#### **9.4.2.2 Secondary Endpoint(s)**

The analysis of the secondary objectives will be presented in the SAP.

#### **9.4.3 Safety**

Safety analyses will be performed separately for the different phases of the study using the 3 safety sets defined above, as appropriate. Safety data will be presented primarily using descriptive statistics, by treatment arm and study phase.

#### **Adverse Events**

Adverse events will be coded using the most recent version of the MedDRA that will have been released for execution at AstraZeneca.

A high-level overview of AEs will be presented for each treatment group and will include the number and percentage of participants with any AE, AEs with outcome of death, SAEs, and AEs leading to discontinuation of SZC/placebo or lisinopril/valsartan.

Adverse events will be presented for each treatment group by system organ class and/or preferred term, covering number and percentage of participants reporting at least one event and number of events where appropriate. Similar tables will be created for SAEs, discontinuations due to AE, and AEs with the outcome of death. Separate AE tables will be provided to illustrate AE pattern with respect to causal relationship as assessed by the investigator, as well as the intensity of AEs. Key information will be presented for participants with AEs with outcome of death, serious AEs, and AEs leading to discontinuation of SZC/placebo. Adverse events occurring during the screening period will be presented in a listing.

#### **Vital Signs, Laboratory Evaluations, and ECG**

The distribution of the measurements over time will be illustrated by presenting the summary statistics (mean, SD, median, minimum, maximum) of the values obtained at the study visits, as well as change from baseline to each of the respective visits. The occurrence of extreme measurements, eg, measurements falling outside pre-defined criteria at any point during a study phase, or measurements judged to be abnormal by the investigator, will be summarised by means of frequencies and percentages.

### **Events of Hypokalaemia and Oedema**

A tabulated overview of oedema-related AEs will be presented, with oedema-related AE defined through the following preferred terms: fluid overload, fluid retention, generalised oedema, hypervolaemia, localised oedema, oedema, oedema peripheral, peripheral swelling.

Instances of  $S-K < 3.5$  mmol/L at particular visits, as well as the number and percentage of participants with  $S-K < 3.5$  mmol/L at any point during a study phase, will be tabulated. Instances of  $S-K < 3.0$  and  $< 2.5$  mmol/L will be presented in a similar manner.

### **9.5 Interim Analyses**

There are no interim analyses planned in this study.

### **9.6 Data Monitoring Committee**

An independent DMC that is unblinded to treatment allocation will be responsible for safeguarding the interests of the participants throughout the study. For details on the DMC, see Appendix A 5.

## **10 SUPPORTING DOCUMENTATION AND OPERATIONAL CONSIDERATIONS**

## Appendix A Regulatory, Ethical, and Study Oversight Considerations

### A 1 Regulatory and Ethical Considerations

- This study will be conducted in accordance with the protocol and with the following:
  - Consensus ethical principles derived from international guidelines including the Declaration of Helsinki and Council for International Organizations of Medical Sciences (CIOMS) International Ethical Guidelines
  - Applicable International Council for Harmonisation (ICH) Good Clinical Practice (GCP) Guidelines
  - Applicable laws and regulations
- The protocol, protocol amendments, informed consent form (ICF), Investigator's Brochure, and other relevant documents (eg, advertisements) must be submitted to an Institutional Review Board (IRB)/Independent Ethics Committee (IEC) by the investigator and reviewed and approved by the IRB/IEC before the study is initiated.
- Any amendments to the protocol will require IRB/IEC and applicable Regulatory Authority approval before implementation of changes made to the study design, except for changes necessary to eliminate an immediate hazard to study participants.
- AstraZeneca will be responsible for obtaining the required authorisations to conduct the study from the concerned Regulatory Authority. This responsibility may be delegated to a Contract Research Organisation (CRO) but the accountability remains with AstraZeneca.
- The investigator will be responsible for providing oversight of the conduct of the study at the site and adherence to requirements of 21 Code of Federal Regulations (CFR), ICH guidelines, the IRB/IEC, European Regulation 536/2014 for clinical studies (if applicable), European Medical Device Regulation 2017/745 for clinical device research (if applicable), and all other applicable local regulations.

### Regulatory Reporting Requirements for Serious Adverse Events

- Prompt notification by the investigator to the Sponsor of a serious adverse event (SAE) is essential so that legal obligations and ethical responsibilities towards the safety of participants and the safety of a study intervention under clinical investigation are met.
- The Sponsor has a legal responsibility to notify both the local regulatory authority and other regulatory agencies about the safety of a study intervention under clinical investigation. The Sponsor will comply with country-specific regulatory requirements relating to safety reporting to the regulatory authority, IRBs/IECs, and investigators.
- For all studies except those utilising medical devices, investigator safety reports must be prepared for suspected unexpected serious adverse reactions (SUSAR) according to local regulatory requirements and Sponsor policy and forwarded to investigators as necessary.
  - European Medical Device Regulation 2017/745 for clinical device research (if applicable), and all other applicable local regulations
- An investigator who receives an investigator safety report describing an SAE or other specific safety information (eg, summary or listing of SAEs) from the Sponsor will

review and then file it along with the Investigator's Brochure and will notify the IRB/IEC, if appropriate according to local requirements.

## **A 2 Financial Disclosure**

Investigators and sub-investigators will provide the Sponsor with sufficient, accurate financial information as requested to allow the Sponsor to submit complete and accurate financial certification or disclosure statements to the appropriate regulatory authorities. Investigators are responsible for providing information on financial interests during the course of the study and for 1 year after completion of the study.

## **A 3 Informed Consent Process**

- The investigator or his/her representative will explain the nature of the study to the participant or his/her legally authorised representative and answer all questions regarding the study.
- Participants must be informed that their participation is voluntary and they are free to refuse to participate and may withdraw their consent at any time and for any reason during the study. Participants or their legally authorised representative will be required to sign a statement of informed consent that meets the requirements of 21 CFR 50, local regulations, ICH guidelines, Health Insurance Portability and Accountability Act (HIPAA) requirements, where applicable, and the IRB/IEC or study centre.
- The medical record must include a statement that written informed consent was obtained before the participant was enrolled in the study and the date the written consent was obtained. The authorised person obtaining the informed consent must also sign the ICF.
- Participants must be re-consented to the most current version of the ICF(s) during their participation in the study.
- A copy of the ICF(s) must be provided to the participant or the participant's legally authorised representative.

Participants who are rescreened are required to sign a new ICF.

## **A 4 Data Protection**

- Participants will be assigned a unique identifier by the Sponsor. Any participant records or datasets that are transferred to the Sponsor will contain the identifier only; participant names or any information which would make the participant identifiable will not be transferred.
- The participant must be informed that his/her personal study-related data will be used by the Sponsor in accordance with local data protection law. The level of disclosure and use of their data must also be explained to the participant in the informed consent.
- The participant must be informed that his/her medical records may be examined by Clinical Quality Assurance auditors or other authorised personnel appointed by the Sponsor, by appropriate IRB/IEC members, and by inspectors from regulatory authorities.

## **A 5 Committees Structure**

### **A 5.1 Executive Committee**

Together with AstraZeneca, the Executive Committee will be responsible for the final overall study design, including the development of the study protocol and any protocol amendments needed during the study, liaison with the Data Monitoring Committee (DMC), as needed, development of the charter, and supervision, interpretation, and reporting (presentations at international congresses and publications in peer reviewed journals) of the study.

The Executive Committee will make recommendations to AstraZeneca with regard to early stopping or modifications of the study based on the information received from the DMC. The Executive Committee will be comprised of designated international academic leaders and non-voting members of the Sponsor and will operate under an Executive Committee charter.

### **A 5.2 Data Monitoring Committee**

An independent DMC will be appointed. The DMC will be responsible for monitoring the progress of the study with respect to randomisation, compliance, and follow up, as well as for reviewing the unblinded data for evidence of benefit or harm. The DMC can make recommendations to the Sponsor and the Executive Committee to alter or terminate all or part of the trial. A DMC charter will be prepared to detail precise roles and responsibilities and procedures to ensure maintenance of the blinding and integrity of the study in the review of accumulating data and interactions with the Executive Committee.

## **A 6 Dissemination of Clinical Study Data**

A description of this clinical study will be available on <http://astrazenecagrouptrials.pharmacm.com> and <http://www.clinicaltrials.gov> as will the summary of the study results when they are available. The clinical study and/or summary of study results may also be available on other websites according to the regulations of the countries in which the study is conducted.

## **A 7 Data Quality Assurance**

- All participant data relating to the study will be recorded on electronic case report form (eCRF) unless transmitted to the Sponsor or designee electronically (eg, laboratory data). The investigator is responsible for verifying that data entries are accurate and correct by electronically signing the eCRF.
- The investigator must maintain accurate documentation (source data) that supports the information entered in the eCRF.
- The investigator must permit study-related monitoring, audits, IRB/IEC review, and regulatory agency inspections, and provide direct access to source data documents.

- Monitoring details describing strategy (eg, risk-based initiatives in operations and quality such as Risk Management and Mitigation Strategies and Analytical Risk-Based Monitoring), methods, responsibilities, and requirements, including handling of non-compliance issues and monitoring techniques (central, remote, or on-site monitoring) are provided in the in the Monitoring Plan and Clinical Trial Agreement.
- The Sponsor or designee is responsible for the data management of this study including quality checking of the data.
- The Sponsor assumes accountability for actions delegated to other individuals (eg, CROs).
- Study monitors will perform ongoing source data verification to confirm that data entered into the eCRF by authorised site personnel are accurate, complete, and verifiable from source documents; that the safety and rights of participants are being protected; and that the study is being conducted in accordance with the currently approved protocol and any other study agreements, ICH GCP, and all applicable regulatory requirements.
- Records and documents, including signed ICFs, pertaining to the conduct of this study must be retained by the investigator for 25 years after study completion unless local regulations or institutional policies require a longer retention period. No records may be destroyed during the retention period without the written approval of the Sponsor. No records may be transferred to another location or party without written notification to the Sponsor.

## **A 8        Source Documents**

- Source documents provide evidence for the existence of the participant and substantiate the integrity of the data collected. Source documents are filed at the investigator's site.
- Data entered in the eCRF that are transcribed from source documents must be consistent with the source documents or the discrepancies must be explained. The investigator may need to request previous medical records or transfer records, depending on the study. Also, current medical records must be available.
- Definition of what constitutes source data can be found in ICH GCP Section 1.52 Source Documents.

## **A 9        Study and Site Start and Closure**

The study start date is the date on which the clinical study will be open for recruitment of participants.

The first act of recruitment is the first site open and will be the study start date.

The Sponsor designee reserves the right to close the study site or terminate the study at any time for any reason at the sole discretion of the Sponsor. Study sites will be closed upon study completion. A study site is considered closed when all required documents and study supplies have been collected and a study-site closure visit has been performed.

The investigator may initiate study-site closure at any time, provided there is reasonable cause and sufficient notice is given in advance of the intended termination.

Reasons for the early closure of a study site by the Sponsor or investigator may include but are not limited to:

- Failure of the investigator to comply with the protocol, the requirements of the IRB/IEC or local health authorities, the Sponsor's procedures, or GCP guidelines.
- Inadequate recruitment of participants by the investigator.
- Discontinuation of further study intervention development.

If the study is prematurely terminated or suspended, the Sponsor shall promptly inform the investigators, the IECs/IRBs, the regulatory authorities, and any CRO(s) used in the study of the reason for termination or suspension, as specified by the applicable regulatory requirements. The investigator shall promptly inform the participant and should assure appropriate participant therapy and/or follow-up.

Participants from terminated sites will have the opportunity to be transferred to another site to continue the study.

## **A 10      Publication Policy**

- The results of this study may be published or presented at scientific meetings. If this is foreseen, the investigator agrees to submit all manuscripts or abstracts to the Sponsor before submission. This allows the Sponsor to protect proprietary information and to provide comments.
- The Sponsor will comply with the requirements for publication of study results. In accordance with standard editorial and ethical practice, the Sponsor will generally support publication of multicentre studies only in their entirety and not as individual site data. In this case, a coordinating investigator will be designated by mutual agreement.
- Authorship will be determined by mutual agreement and in line with International Committee of Medical Journal Editors authorship requirements.

## Appendix B RAASi Therapy Considerations for Inclusion into the Study and Dosing of Lisinopril and Valsartan

### B 1 Guide for Change of Other RAASi therapy into an Equivalent Dose Range for Lisinopril or Valsartan

Other ACEi or ARB SoC dose a	Lisinopril (mg) b	Valsartan (mg) b
None or starting daily dose	10 (5) c	80
Mid-range daily dose (doses between starting and maximum dose if applicable)	20 (10) c	160
Maximum daily dose	20 (20) c	160

a See Appendix B 2 for starting, mid-range (if applicable), and maximum daily dose of each individual ACEi/ARB drug.

b Starting dose may differ per local labels. For example, in Japan, where starting doses are lower than specified above, the following would apply:

- Starting: lisinopril 10 mg; valsartan 40 mg
- Mid-range: lisinopril 20 mg; valsartan 80 mg
- Maximum: lisinopril 20 mg; valsartan 160 mg

c If eGFR  $\geq$  10 to  $\leq$  30 mL/min/1.73m^2 or participant is on diuretics, or per local label, lisinopril starting, mid-range, and maximum are 5, 10, and 20 mg, respectively.

ACEi, angiotensin converting enzyme inhibitor; ARB, angiotensin II receptor blocker; eGFR, estimated glomerular filtration rate; SoC, standard of care.

For subsequent up-titration of lisinopril or valsartan during the run-in phase, see Sections 6.6.2 and 6.6.3.

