As soon as the shortage is resolved, valsartan should be restarted at a dose determined by using the conversion table in Appendix B 1 unless in the investigator's judgment a change in dose is required. Every effort should be made to maximise the doses of valsartan and of irbesartan if the latter needs to be used because of a valsartan shortage.

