**B 2 RAASi Dose Equivalence Table**

Drug	Starting daily dose	Mid-range daily dose (if applicable)	Maximum daily dose
ARB			
Valsartan a	80 mg	160 mg	320 mg
Losartan a	50 mg	-	100 mg
Olmesartan	20 mg	-	40 mg
Azilsartan	20 – 80 mg	40 mg	80 mg
Candesartan	16 mg	-	32 mg
Irbesartan a	150 mg	-	300 mg
Telmisartan	40 mg	-	80 mg
ACEi			
Lisinopril a	10 mg	20 mg	40 mg
Ramipril CrCl < 40 mL/min: 25% of normal dose	2.5 mg	5 mg, 10 mg	20 mg
Perindopril b CrCl < 30 mL/min: not recommended	2 mg	4 mg	8 mg
Benazepril	10 mg CrCl < 30 mL/min: 5 mg	20 mg, 40 mg	80 mg
Captopril CrCl 10-50 mL/min: 75% of normal dose CrCl < 10 mL/min: 50% of normal dose	12.5 – 25 mg bid to tid	12.5 mg tid 25 mg, 37.5 mg bid to tid 50 mg bid	Usually 50 mg tid (may go up to 450 mg)
Enalapril	5 mg CrCl ≤ 30 mL/min: 2.5 mg	10 mg, 20 mg	40 mg
Fosinopril	10 mg	20 mg, 40 mg	80 mg
Quinapril	10 mg CrCl 61-89 mL/min: 10 mg CrCl 30-60 mL/min: 5 mg CrCl 10-29 mL/min: 2.5 mg	20 mg, 40 mg	80 mg
Trandolapril	1 mg CrCl < 30 mL/min: 0.5 mg	2 mg	4 mg

NOTE: Dosage recommendations are based on KDIGO guidelines ([KDIGO 2020](#))/information from package inserts registered in the United States and may differ across countries and regulatory authorities.

a Doses may differ per local labels. For example, valsartan starting dose can be 40 mg; losartan starting dose can be 25 mg; irbesartan starting dose can be 50 or 75 mg; irbesartan maximum dose can be 200 mg (eg, Japan); lisinopril starting dose can be 2.5 or 5 mg.

b Refers to perindopril erbumine (tablet strength may differ depending on perindopril salt).

ACEi, angiotensin converting enzyme inhibitor; ARB, angiotensin II receptor blocker; bid, twice daily; CrCl, creatinine clearance; eGFR, estimated glomerular filtration rate; KDIGO, Kidney Disease: Improving Global Outcomes; tid, three times daily.

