### B 3 Definitions of RAASi Adequate Dose

Renin-angiotensin-aldosterone system inhibitor (RAASi) adequate dose levels are defined below. Doses lower than the ones listed below are considered as suboptimal.

The definition of “limited RAASi therapy” for purposes of inclusion in the study (Section 5.1) = no or suboptimal RAASi.

ARB	Adequate daily dose a, b	ACEi	Adequate daily dose a, b
Valsartan	160 - 320 mg	Lisinopril	20 - 40 mg
Losartan	50 - 100 mg	Ramipril CrCl < 40 mL/min: 25% of normal dose	10 - 20 mg
Olmesartan	40 mg	Perindopril c CrCl < 30 mL/min: not recommended	8 mg
Azilsartan	40 - 80 mg	Benazepril	20 - 80 mg
Candesartan	32 mg	Captopril CrCl 10-50 mL/min: 75% of normal dose CrCl < 10 mL/min: 50% of normal dose	37.5 bid - 50 mg tid
Irbesartan	300 mg	Enalapril	10 - 40 mg
Telmisartan	80 mg	Fosinopril	20 - 80 mg
		Quinapril	20 - 80 mg
		Trandolapril	2 - 4 mg

NOTE: Adequate dose level definitions are based on KDIGO guidelines ([KDIGO 2020](#))/information from package inserts registered in the United States and may differ across countries and regulatory authorities.

a Normokalaemic participants with hypertension or primary glomerular diseases with nephrotic range proteinuria (> 3.5 g/24 hours) who are at high risk of hyperkalaemia, not taking maximal RAASi doses as per local label but currently receiving doses in the range considered adequate in this table can be included in the normokalaemic cohort if in the investigator's judgment the current RAASi dose is not optimal for their condition. In these participants, it is expected that RAASi doses will be up-titrated to maximal during the run-in phase.

b Where a range is indicated, any daily dose within that range is considered an adequate daily dose.

c Refers to perindopril erbumine (tablet strength may differ depending on perindopril salt).

[figure not shown]
ACEi, angiotensin converting enzyme inhibitor; ARB, angiotensin II receptor blocker; bid, twice daily; CrCl, creatinine clearance; RAASI, renin-angiotensin-aldosterone system inhibitor; tid, three times daily.

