## **Appendix E    Temporary Irbesartan Use in the Event of a Local Valsartan Shortage**

**Refer to this Appendix only if valsartan needs to be temporarily substituted with irbesartan during valsartan shortage.**

The study is designed to use valsartan as the selected ARB therapy adjunct to SZC. However, if an actual shortage of valsartan in a local market jeopardises the ability of participants to enter or continue in the study, valsartan can be temporarily substituted with irbesartan until the shortage of valsartan is resolved.

During treatment with irbesartan, the same procedures indicated for valsartan discontinuation (Section 7) and efficacy, safety, and other assessments (Section 8) must be followed.

As soon as the shortage is resolved, valsartan should be restarted at a dose determined by using the conversion table in Appendix B 1, unless in the investigator's judgment a change in dose is required. Every effort should be made to maximise the doses of valsartan and of irbesartan if the latter needs to be used because of a valsartan shortage.

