#### **E 4        Investigational Medicinal Product (Irbesartan)**

See Section [6.1](#) for the study interventions (investigational products) SZC/placebo, lisinopril/valsartan of the study.

The study intervention (investigational product) irbesartan to be administered in this study during valsartan shortage is presented below.

Intervention name/ Characteristic	Irbesartan
Type	Drug
Dose formulation	Tablet
Unit dose strength(s) a	75, 150, or 300 mg
Dosage level(s) a	75, 150, or 300 mg QD
Route of administration	Oral
Use	Background intervention
IMP or NIMP	IMP
Provider	Local sourcing preferred. Under certain circumstances when local sourcing is not feasible, irbesartan may be supplied centrally through AstraZeneca.
Packaging and labelling	Provided in original package and labelled in accordance with GMP Annex 13 and per country regulatory requirement. Label text will be translated into local language.

a For Japan, dose levels are 50, 100, or 200 mg QD with unit dose strengths 50 or 100 mg.

GMP, Good Manufacturing Practice; IMP, investigational medicinal product; NIMP, non-investigational medicinal product; QD, once daily.

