#### **E 5        Guide for Change of Other RAASi therapy into an Equivalent Dose Range for Irbesartan**

In the situation that valsartan is not available when a participant should enter the run-in phase, the following instructions will be followed.

- Participants who are not on ACEi or ARB therapy upon entering the run-in phase, and per investigator's judgement are to be initiated on an ARB will be started on irbesartan on the first day of the run-in phase (starting dose as per table below).
- Participants who are on ARB therapy other than irbesartan at screening will have their therapy changed to irbesartan upon entering the run-in phase. See [Appendix B 2](#) for guidance on the dosing equivalences among ARB drugs and irbesartan.

- Participants who are on irbesartan will continue treatment at the same dose.

A participant cannot receive both lisinopril and irbesartan simultaneously and should not take any other ACEi or ARB concomitantly with irbesartan.

The table below applies also for dose equivalent conversion of valsartan to irbesartan at any stage of the study beyond the run-in phase.

Other ARB SoC dose a	Irbesartan (mg) b
None or starting daily dose	75
Mid-range daily dose (doses between starting and maximum dose if applicable)	150
Maximum daily dose	150

a See Appendix B 2 for starting, mid-range (if applicable), and maximum daily dose of each individual ARB drug including valsartan.

b Starting dose may differ per local labels. For example, in Japan, the following would apply:

- Starting: Irbesartan 50 mg if applicable
- Mid-range: Irbesartan 100 mg if applicable
- Maximum: Irbesartan 100 mg if applicable

ARB, angiotensin II receptor blocker; SoC, standard of care.

For subsequent up-titration of irbesartan during the run-in phase, see Appendix E 6.

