## E 6 Irbesartan Dose Titration Steps

Upon entering the run-in phase:

Every effort should be made to increase irbesartan to its maximum dose during the run-in phase. The following dose steps should be used for up-titration:

Dose steps (daily dose)	Irbesartan (mg) a
STEP 1	75
STEP 2	150
STEP 3	300

a Starting dose and dose range may differ per local labels. For example, in Japan, the following would apply:

- STEP 1: Irbesartan 50 mg if applicable
- STEP 2: Irbesartan 100 mg if applicable
- STEP 3: Irbesartan 200 mg if applicable

For up-titration and dose modification strategy of irbesartan during the run-in and maintenance phases, see Sections 6.6.3, 6.6.4, 6.6.5 and follow the same recommendations as for valsartan.

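### Where the printed irbesartan row of Appendix B 2 applies, a participant still on irbesartan 150 mg returns from a valsartan shortage to 80 mg, although Appendix E 5 reaches 150 mg from valsartan 160 mg

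*Protocol*

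**What the plan says.** **Going out.** Appendix E 5 converts a starting, mid-range or maximum ARB dose to irbesartan 75, 150 or 150 mg. It covers participants already on study valsartan: "The table below applies also for dose equivalent conversion of valsartan to irbesartan at any stage of the study beyond the run-in phase". Appendix E 4 gives the study's irbesartan doses as "75, 150, or 300 mg QD", and E 6 makes these STEP 1, 2 and 3. For Japan the doses are 50, 100 and 200 mg ("STEP 2: Irbesartan 100 mg if applicable"). E 6 applies the valsartan titration strategy to irbesartan, and Section 6.6.4 of that strategy calls STEP 2 mid-range.

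**Coming back.** In Section 4.1.3, "valsartan should be restarted at a dose determined by using the conversion table in Appendix B 1 unless" the investigator judges that another dose is needed. Appendix E repeats the rule: "As soon as the shortage is resolved, valsartan should be restarted at a dose determined by using the conversion table in Appendix B 1". Section 4.1.4 carries it into the maintenance phase by reference. B 1 converts starting, mid-range and maximum doses to valsartan 80, 160 and 160 mg. Its footnote a takes the class of the incoming dose from B 2: "See Appendix B 2 for starting, mid-range (if applicable), and maximum daily dose of each individual ACEi/ARB drug". The B 2 row for irbesartan reads 150 mg starting, no mid-range, 300 mg maximum. A footnote to that row adds that, under local labels, the "irbesartan starting dose can be 50 or 75 mg".

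**Adequate dose.** B 3 lists valsartan 160 to 320 mg as adequate and adds: "Doses lower than the ones listed below are considered as suboptimal".

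**Endpoint.** Protocol Section 8.1.2 defines the dosing endpoint as time to the first change to a dose below the one taken at randomisation, whatever the cause. SAP Section 4.2.3 uses the first RAASi dose decrease after randomisation. Neither says how doses of two different drugs are compared.

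**The concern.** Irbesartan 150 mg has two meanings. Going out, it stands in for valsartan 160 mg and is the middle step. Coming back, the printed B 2 row makes it the lowest dose. A participant whose irbesartan has not been changed can therefore leave on 160 mg and return on 80 mg for supply reasons alone.

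That runs against the run-in aim of reaching maximum RAASi doses, and against the repeated instruction to restore and maximise them. It may also feed into secondary endpoint #2, which is meant to show whether SZC helps participants keep their RAASi dose.

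**Working it through.** The plan gives no figure to reproduce. The check is a table look-up.

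**Inputs**
- Valsartan classes (B 2): 80 starting, 160 mid-range, 320 maximum.
- Out (E 5): starting → 75, mid-range → 150, maximum → 150 mg irbesartan.
- Back (B 1): starting → 80, mid-range → 160, maximum → 160 mg valsartan.
- Irbesartan classes, printed B 2 row: 150 starting, 300 maximum. Irbesartan 75 mg is not in that row; I treat it as starting.
- Irbesartan classes, E 6: 75 / 150 / 300 as starting / mid-range / maximum.

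**Step 1: round trip with irbesartan left at its converted dose (mg)**

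| Valsartan before | Irbesartan (E 5) | Class by B 2 row | Valsartan after | Class by E 6 | Valsartan after |
|---|---|---|---|---|---|
| 80 | 75 | starting | 80 | starting | 80 |
| 160 | 150 | starting | **80** | mid-range | 160 |
| 320 | 150 | starting | **80** | mid-range | 160 |

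**Step 2: what belongs to the conflict.** From 160 mg the whole loss of one step (160 → 80) comes from B 2. From 320 mg the loss is two steps, but the first (320 → 160) remains with E 6 classes, because E 5 and B 1 both map a maximum dose to a mid-range one. Only the second (160 → 80) comes from the conflict.

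**Step 3: when 80 mg does not arise**
- With a local-label start of 50 or 75 mg, 150 mg lies between the start and the 300 mg maximum. It is then mid-range and returns 160 mg.
- If irbesartan was raised to 300 mg before the return, it is maximum on either reading and returns 160 mg.
- Japan: valsartan 80 → irbesartan 100 → valsartan 80, so there is no clash. Valsartan 160 → irbesartan 100 → valsartan 80 is the maximum-to-mid-range rule again.
- The investigator may choose another dose.

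**Step 4: time to recover.** Section 6.6.3 allows 2 weeks per up-titration step in the run-in; I assume the same pace later. From 80 mg, regaining 160 mg takes 1 × 2 = 2 weeks and regaining 320 mg takes 2 × 2 = 4 weeks. With E 6 classes the times are 0 and 1 × 2 = 2 weeks.

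**Step 5: endpoint #2 for a participant randomised on 160 mg.** Only the first decrease counts, so the answer depends on how the switch out is treated.

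| How 160 → irbesartan 150 is compared | Switch out counted? | Does the return to 80 add an event? |
|---|---|---|
| Raw mg (150 < 160) | yes | no |
| B 2 classes (mid-range → starting) | yes | no |
| E 6 steps (STEP 2 → STEP 2) | no | yes |
| Irbesartan period ignored | no | yes |

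For a participant randomised on 320 mg, a decrease occurs whether irbesartan 150 mg is classed by B 2 or by E 6, so the conflict adds no event.

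**The case against.** **The 80 mg result is avoidable.** A reader might infer that every return from a shortage goes to 80 mg. The documents do not support that: local labels, up-titration and investigator judgement each prevent it, and the protocol asks for every effort to maximise both drugs. This stands and limits the point to participants still on 150 mg where the printed B 2 row governs. It does not remove the conflict, because the text offers that row as the default while E 4 to E 6 use a 75 mg start.

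**The fall from 320 mg.** A reader might also blame the whole drop from 320 to 80 mg on B 2. Step 2 above shows that half of the two-step loss is a consistent conversion rule, to be followed by re-titration.

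**B 3 could be read the other way.** B 3 accepts only irbesartan 300 mg as adequate, so 150 mg is suboptimal there, and returning it to an adequate valsartan dose may look inconsistent. It is true that the appendices do not agree on 150 mg. But B 3 defines adequate dosing and is not a conversion table, and E 5 has already equated valsartan 160 mg with irbesartan 150 mg. Reading the same pair backwards only restores the earlier dose.

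**Little depends on it.** No shortage or switch is documented. Endpoint #2 is formally tested only after both co-primary hypotheses and secondary objective #1 succeed. The SAP amendment history records premature termination. All of this stands and is why the point is minor.

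**Conclusion.** The conflict is real and rests on the printed tables alone. With the B 2 row as printed and irbesartan still at 150 mg, valsartan 160 mg returns as 80 mg, one step lower and suboptimal under B 3. From 320 mg, one of the two lost steps has this cause. The recovery times assume that the run-in titration pace applies later.

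A reader might infer that the return rule inflates endpoint #2 or distorts its hazard ratio. The documents do not support that. An extra event arises only for participants randomised on 160 mg whose switch out was not already counted, and the number of switches is not given. Nothing ties a shortage to treatment arm, and randomisation is stratified by country. Nor is an effect on the co-primary slopes claimed: those analyses follow a treatment policy for dose changes and use the eGFR data whatever the RAASi dose.

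Severity is minor; confidence in the look-up is high.

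**What to change.** **Protocol Section 4.1.3 and Appendix E.** Add: 'For the return to valsartan, irbesartan 75/150/300 mg (Japan 50/100/200 mg) are read as starting/mid-range/maximum in Appendix B 1, so that 150 mg returns to valsartan 160 mg; valsartan is then re-titrated towards the pre-shortage dose.' The re-titration clause is still needed for participants who were on 320 mg, and in Japan on 160 mg.

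**SAP Section 4.2.3.** Add: 'Where the drug changes, doses are compared by dose step (Appendix E 6 for irbesartan) and not by mg.' A shortage switch from valsartan 160 mg to irbesartan 150 mg is then not a decrease. A participant who actually restarts below the randomised valsartan dose still counts, as Section 8.1.2 requires.

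**Cost.** One sentence in two places of the protocol and one derivation rule in the SAP. Prescribed doses and dates are already recorded, and no extra model is needed. Because the study closed early, the protocol sentence serves only the record or reuse of the text; the SAP rule can still be applied.
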